5.11.10 Electrocardiograms

For quantitative ECG measurements (heart rate, PR interval, QRS duration, QT interval, and corrected QT intervals using Bazett and Fridericia correction methods), values during the double-blind period will be presented by treatment group for all visits.

The Bazett corrected QT (QTcB) will be calculated as

$$QTcB = QT / RR^{0.5}, \text{ where } RR = 60 / \text{HR}.$$

The Fridericia corrected QT (QTcF) will be calculated as

$$QTcF = QT / RR^{0.33}, \text{ where } RR = 60 / \text{HR}.$$

The following summaries and listings will be provided:

- A summary of 12-lead by treatment group at each specified visit.
- The number and percentage of subjects with a QTc (using Bazett and Fridericia corrected) of $\leq 450\text{ms}$, >450 to $\leq 480\text{ms}$, >480 to $\leq 500\text{ms}$, and $>500\text{ms}$ will be summarized by treatment group at each specified visit.
- The number and percentage of subjects with a QTc (using Bazett and Fridericia corrected) of an increase from baseline of >0 to $\leq 30\text{ms}$, >30 to $\leq 60\text{ms}$, and $>60\text{ms}$ will be summarized by treatment group at each specified visit.
- The number and percentage of subjects with PR interval values $\leq 120\text{ms}$, >120 to $\leq 220\text{ms}$, and $>220\text{ms}$, and the number and percentage of subjects with QRS interval values $\leq 60\text{ms}$, >60 to $\leq 120\text{ms}$, and $>120\text{ms}$ will be presented by treatment group at each specified visit.
- The number and percentage of subjects with abnormal ECG findings at Visit 1, and the number and percentage of subjects in the SAF with an abnormal ECG after the start of dose of study medication drug will be summarized by visit and treatment group in separate tables. Subjects with a clinically relevant abnormal ECG as determined by the investigator will be listed.

- A summary of incidence of treatment-emergent abnormality 12-lead ECG findings after start of study drug by treatment group.
- A by-subject listing of abnormal 12-lead ECG data will be provided.

5.11.11 Vital Signs, Physical Findings and Other Observations Related to Safety

Noninvasive pulse rate, temperature, systolic blood pressure (SBP) and diastolic blood pressure (DBP) will be measured at visits with the subject in a sitting position after at least 10 minutes at rest, according to the tabular schedule of study procedures in the protocol. Summary statistics of the actual measurement and their changes from baseline will be presented by treatment group at each specified visit.

In addition, summary statistics for the actual value and change from baseline will be presented by treatment group for all visits during the double-blind period.

Abnormal vital signs will be summarized by treatment group for double-blind and extension period.

Abnormal vital sign criteria as follows:

- diastolic blood pressure [DBP]: <50, >90, >100 mmHg
- systolic blood pressure [SBP]: <90, >140, >160 mmHg
- pulse rate [PR]: <60, >100 bpm
- Temperature: <36.0, >38.0

The following summaries and listings will be provided:

- A summary of pulse rates, temperature, blood pressure and change from baseline by treatment group and visit.
- The number and percentage of subjects with abnormal vital signs during double-blind period and extension period by treatment group.
- A by-subject listing of vital signs.

5.12 Pharmacokinetics and Pharmacodynamics

The serum SA237 concentrations will be reported using the PK-PPS. The PD variables (IL-6, sIL-6R, hsCRP, anti-AQP4Ab, plasmablast) will be reported using the SAF population.

To determine the concentrations of SA237, serum samples will be drawn at various time points throughout the study. At Week 0, blood specimens for PK and PD samples will be collected prior to first dose administration of study drug (blank value). At other visits, PK and PD samples will be collected along with hematology samples at any time prior to study drug administration according to the Schedule of Study assessments.

To support the Japanese BLA, the following reports will be produced. Concentration for SA237 and PD variables in serum will be listed and summarized using descriptive statistics (including geometric mean and CV%, arithmetic mean and SD, median, observed maximums and minimums, and sample size). Arithmetic mean \pm SD serum concentration-

time profile and combined all subjects serum concentration-time profiles (spaghetti plot) will be plotted using linear and semi-log scale. In addition, individual serum concentration-time profile will be plotted for each subjects using linear and semi-log scale.

Concentration for SA237 and PD variables (absolute values as well as change from baseline) in serum will be summarized using descriptive statistics and arithmetic mean \pm SD serum concentration-time profile will be plotted by following subgroup using linear scale.

Samples that were excluded from the summary statistics will be marked in the listing.

Summary tables, figures, and listings of SA237 concentration and PD variables will be provided as follows:

- Summaries of concentrations of SA237 by visit will be presented by age category, Japanese/non-Japanese, relapse/no-relapse, ADA status, and overall.
- Summary of concentration of IL-6, sIL-6R, and hsCRP by visit will be presented by age category, Japanese/non-Japanese, relapse/no-relapse and overall in each of treatment group.
- Summary of titer for anti AQP4 antibody status, Plasmablast (Plasmablasts/CD19+ (%), Plasmablasts/CD45+ (%), and Plasmablasts (cells/uL)), and CD19+ cells (CD19+/CD45+ (%) and CD19+ (cells/uL)) by visit will be presented by NMO/NMOSD and AQP4 Status, relapse/no-relapse and overall in each of treatment group.

*Plasmablast and CD19+ cells will be calculated by following equation

➤ $\text{Plasmablasts (cells/uL)} = \text{CD45+Abs} * \text{Plasmablasts/CD45+ (\%)}$

➤ $\text{CD19+ (cells/uL)} = \text{CD45+Abs} * \text{CD19+/CD45+ (\%)}$

- A by-subject listing of concentration for SA237 in serum.
- A by-subject listing of IL-6, sIL-6R, and hsCRP
- A by-subject listing of anti-AQP4 antibody (positive/negative and titer)
- Plasmablast (Plasmablasts/CD19+(%), Plasmablasts/CD45+(%), and Plasmablast (cells/uL)), and CD19+ cells (CD19+/CD45+(%) and CD 19+ (cells/uL))
- A by-subject spaghetti plot of concentration for SA237 in serum by subgroup (age category, Japanese/non-Japanese, relapse/no-relapse, ADA status) using linear scale and overall using linear and semi log scale.
- A by-subject spaghetti plot of the absolute value and the change from baseline for concentration of IL-6, sIL-6R, and hsCRP by treatment group using linear and semi log scale.

- A by-subject spaghetti plot of the absolute value for concentration of IL-6, sIL-6R, and hsCRP by subgroup (age category, Japanese/non-Japanese, relapse/no-relapse, ADA status) in each of treatment group using linear scale
- A by-subject spaghetti plot of the absolute value for concentration of IL-6, sIL-6R, and hsCRP by treatment group in each subgroup (age category, Japanese/non-Japanese, relapse/no-relapse, ADA status) using linear scale
- A by-subject spaghetti plot of the absolute value and the change from baseline for titer of anti-AQP4 antibody, Plasmablast (Plasmablasts/CD19+ (%), Plasmablasts/CD45+ (%), and Plasmablasts (cells/uL)), and CD19+ cells (CD19+/CD45+ (%), and CD19+ (cells/uL)) by treatment group using linear and semi-log scale
- A by-subject spaghetti plot of the absolute value for titer of anti-AQP4 antibody, Plasmablast (Plasmablasts/CD19+ (%), Plasmablasts/CD45+ (%), and Plasmablasts (cells/uL)), and CD19+ cells (CD19+/CD45+ (%), and CD19+ (cells/uL)) by subgroup (NMO/NMOSD and AQP4 Status, relapse/no-relapse) in each of treatment group using linear scale.
- A by-subject spaghetti plot of the absolute value for titer of anti-AQP4 antibody, Plasmablast (Plasmablasts/CD19+ (%), Plasmablasts/CD45+ (%), and Plasmablasts (cells/uL)), and CD19+ cells (CD19+/CD45+ (%), and CD19+ (cells/uL)) by treatment group in each subgroup (NMO/NMOSD and AQP4 Status, relapse/no-relapse) using linear scale.
- An Arithmetic mean \pm SD plot of concentration for SA237 in serum by subgroup (age category, Japanese/non-Japanese, relapse/no-relapse, ADA status) using linear scale and overall using linear and semi log scale.
- An Arithmetic mean \pm SD plot of the absolute value and the change from baseline for concentration of IL-6, sIL-6R, and hsCRP by treatment group using linear and semi-log scale.
- An Arithmetic mean \pm SD plot of the absolute value for concentration of IL-6, sIL-6R, and hsCRP by subgroup (age category, Japanese/non-Japanese, relapse/no-relapse, ADA status) in each of treatment group using linear scale.
- An Arithmetic mean \pm SD plot of the absolute value for concentration of IL-6, sIL-6R, and hsCRP by treatment group in each subgroup (age category, Japanese/non-Japanese, relapse/no-relapse, ADA status) using linear scale
- An Arithmetic mean \pm SD plot of the absolute value and the change from baseline for titer of anti-AQP4 antibody, Plasmablast (Plasmablasts/CD19+ (%), Plasmablasts/CD45+ (%), Plasmablasts (cells/uL)), and CD19+ cells (CD19+/CD45+ (%) and CD19+ (cells/uL)) by treatment group using linear and semi-log scale

- An Arithmetic mean \pm SD plot of the absolute value for titer of anti-AQP4 antibody, Plasmablast (Plasmablasts/CD19+ (%), Plasmablasts/CD45+ (%), Plasmablasts (cells/uL)), and CD19+ cells (CD19+/CD45+ (%) and CD19+ (cells/uL)) by subgroup (NMO/NMOSD and AQP4 Status, relapse/no-relapse) in each of treatment group using linear scale
- An Arithmetic mean \pm SD plot of the absolute value for titer of anti-AQP4 antibody, Plasmablast (Plasmablasts/CD19+ (%), Plasmablasts/CD45+ (%), Plasmablasts (cells/uL)), and CD19+ cells (CD19+/CD45+ (%) and CD19+ (cells/uL)) by treatment group in each subgroup (NMO/NMOSD and AQP4 Status, relapse/no-relapse) using linear scale.
- A by-subject listing of actual doses, date and time of sampling, visit, relative day, and the accession number.
- Scatter plot of anti-AQP4 antibody titer versus plasmablast (Plasmablasts/CD19+ (%), Plasmablasts/CD45+ (%), Plasmablasts (cells/uL)) will be presented at Weeks 0, 2 and 4, 8, 12, 24, and Q24W. When the data of anti-AQP4 antibody is negative, put "1" as a titer for negative samples and replace to "BLQ".
- Scatter plots of serum SA237 concentration versus body weight at weeks 2, 4, Q4W respectively.

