7.6 Rule for summary of titer for anti AQP4 antibody status

Titer for anti AQP4 antibody status except screening visit will be replaced by following rule. This rule will apply to throughout TFL.

- If value is "<16", value will be replaced as 4.
- If titer is character (eg. ">16384", ">65536" except "<16") or titer is numeric more than 16384 (eg. "65536", "262144"), value will be replaced as 65536.

7.7 SAS Codes:

Log-rank test:

```
proc lifetest data=final;  
  
    time DURATION*STATUS (0);  
  
    strata ARR REGEON / group=TREATMENT;  
  
    ods output test=_logrank;  
  
run;
```

Cox Regression Model:

```
proc phreg data=final;  
  
    class TREATMENT/descending;  
  
    Model DURATION*STATUS(0)=TREATMENT / ties=exact rl;  
  
    strata ARR REGION;  
  
    ods output parameterEstimates=est;  
  
run;
```

Mixed effect Model Repeat Measurement (MMRM)

```
proc mixed data=VAS method=REML;  
  
    class REGION TREATMENT VISIT USUBJIDARR;  
  
    model CHG = BASE TREATMENT REGION VISIT ARR  
    TREATMENT*VISIT/ddfm=KR;  
  
    repeated VISIT / type=un subject = USUBJID;  
  
    lsmeans TREATMENT*VISIT / pdiff cl;
```

```
ods output lsmeans = lsm; * contains the adjusted means;  
ods output diffs = dif; * contains treatment differences;  
  
run;
```

ANCOVA:

```
proc mixed data=;  
  
class TREATMENT ARR REGION;  
  
model CHG_BL=TREATMENT BASELINE ARR REGION;  
  
lsmeans TREATMENT / pdiff cl;  
  
run;
```

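### PD change from baseline in SAP 5.12 has no ratio or log definition: read as a difference, its semi-log plots can show only rises, and the mean titre change can be dominated by top-titre patients

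*SAP*

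**What the plan says.** SAP 5.12 says that "PD variables (absolute values as well as change from baseline) in serum will be summarized using descriptive statistics". The list of outputs that follows asks for two kinds of change plot by treatment group.

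- By-subject: "A by-subject spaghetti plot of the absolute value and the change from baseline for concentration of IL-6, sIL-6R, and hsCRP" and, separately, "A by-subject spaghetti plot of the absolute value and the change from baseline for titer of anti-AQP4 antibody" together with plasmablasts and CD19+ cells.
- Arm level: each item opens "An Arithmetic mean" and continues with the SD. One covers IL-6, sIL-6R and hsCRP. The other is a "plot of the absolute value and the change from baseline for titer of anti-AQP4 antibody", with plasmablasts and CD19+ cells, and ends "by treatment group using linear and semi-log scale".

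The semi-log request covers the change as well as the absolute value, with no exception. No part of the SAP defines PD change as a ratio or a log difference. SAP 7.6 sets the titre range: entries reported as below 16 become 4. For all entries above 16384, whether numeric or reported with a greater-than sign, the "value will be replaced as 65536".

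SAP 5.12 also lists the geometric mean and median for PD variables, and plans absolute-value plots on both scales.

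**The concern.** There are two separate difficulties.

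The first is the axis. A fall is a negative number and an unchanged value is zero; neither has a logarithm. A semi-log plot of differences therefore leaves out every patient or visit that did not rise. The protocol itself points to falls for some of these markers: section 3.2.2 refers to a reduction of plasmablasts as part of satralizumab's mechanism, and section 5.1.1.1 says that the drug suppresses increases in CRP. For those markers the figure would omit the expected direction.

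The second is the weight given to high titres. Titre is a multiplicative scale. Averaging differences gives a patient near the ceiling far more weight than a patient in mid-range for the same fold change. The arm-level figure could then describe one or two patients, and could put the arms in the wrong order.

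**Working it through.** The plan states no figure on this point, so there is none to reproduce. The check is arithmetic on titres after the SAP 7.6 substitutions.

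**Inputs.** Lowest and highest analysed titre: 4 and 65536 (SAP 7.6). Arm size: about 35 (SAP 5.14). With AQP4-negative adults capped at about 30% (Protocol 4.1), about 0.7 × 35 = 24.5 seropositive patients per arm, so n = 24 is also run.

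**Assumptions.** Titres lie on fourfold steps, which fits the values named in SAP 7.6 (4, 16, 16384, 65536, 262144 are all powers of 4). Change is a difference. The typical baseline titre *b* is not given in the documents, so it is varied.

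**Weight of one step.** (65536 − 16384) / (1024 − 256) = 49,152 / 768 = 64.

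**One riser.** All but one patient fall fourfold from *b* (change −0.75*b*), and one rises from 16384 to 65536 (+49,152).

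Mean change = [49,152 − (n − 1) × 0.75*b*] / n

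| Typical *b* | n = 35 | n = 24 |
|---|---|---|
| 256 | +1,218 | +1,864 |
| 1024 | +658 | +1,312 |
| 4096 | −1,580 | −896 |
| 16384 | −10,533 | −9,728 |

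For example, with n = 35 and *b* = 1024: (49,152 − 34 × 768) / 35 = 23,040 / 35 = 658. The mean is positive when *b* < 65,536 / (n − 1), that is below about 1,928 for n = 35 or 2,849 for n = 24. On the fourfold grid the sign reverses up to 1024 and not from 4096. The median change is negative in every row. The geometric mean ratio does not depend on *b*: 4^(−33/35) = 0.27 for n = 35 and 4^(−22/24) = 0.28 for n = 24.

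A riser one step lower (4096 to 16384, +12,288) has less effect. At *b* = 1024 the mean stays negative (−395 and −224). At *b* = 256 it is positive (+165 and +328).

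**One faller.** In the placebo arm one patient falls from 65536 to 16384 and the rest do not change. Mean change is −49,152 / 35 = −1,404, or −49,152 / 24 = −2,048. In the active arm every patient falls from 1024 to 256, so the mean is −768. The arithmetic mean ranks placebo as the larger fall. The geometric mean ratios are 0.96 (n = 35) or 0.94 (n = 24) for placebo and 0.25 for active. At *b* = 4096 the active mean is −3,072 and the order is correct.

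**Log axis.** Every fall gives a change below 0 and every unchanged value gives 0. Only positive changes can be drawn, for any of the six variables. This step needs no assumption about the data, only the reading of change as a difference.

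**The case against.** The strongest reply is that the planned outputs already contain what is needed. Semi-log by-subject plots of the absolute titre show each fourfold fall at the same height. The linear plots of change show falls. The median is among the planned statistics. The visit geometric mean divided by the baseline geometric mean equals the geometric mean ratio. PD is also descriptive: SAP 5.10.1.4 places only TFR, VAS pain and FACIT fatigue in the test hierarchy.

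Most of this stands, and it limits the point to the change-from-baseline output. The geometric-mean argument stands only if the same patients contribute at both visits. That fails as relapsing patients leave the double-blind period (Protocol 4.5.3.3). A geometric mean of signed differences does not exist.

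It can also be said that the SAP never defines PD change as a subtraction, and that the semi-log axis hints at a ratio. That is fair; subtraction is the ordinary reading, not a stated rule. But where the SAP wants another scale it says so: logMAR conversion for visual acuity (5.10.1.12), a peak-to-baseline ratio for ADA titre (5.13), percentage change for laboratory values (7.1). An edit is needed on either reading.

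A reader might infer that one high-titre patient will reverse the arm comparison. The documents do not support that: they give no titre distribution, and reversal in the cases above stops between 1024 and 4096. A reader might also infer that the SAP 7.6 ceiling should be lifted, because a fall from 262144 to 65536 is analysed as no change. That loss is real. But the listed entries include results reported only as above 16384 or above 65536. Keeping 262144 as measured while an entry above 65536 becomes 65536 would create false fourfold rises and falls.

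**Conclusion.** The point holds as a cheap improvement to descriptive PD output. It is certain that change is undefined and that a semi-log axis is requested for it; if change is a difference, those figures can show only rises. It is conditional that the arithmetic mean titre change misorders the arms. This depends on the fourfold grid and on typical titres of about 1024 or lower, with one patient making a step at the top of the scale. Size was worked out for titre only; for plasmablasts, CD19+ cells, IL-6, sIL-6R and hsCRP only the axis point is shown.

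A reader might conclude that the drug's PD effect would be hidden, or that the efficacy result is at risk. Neither follows: medians and absolute-value semi-log plots remain informative, and no efficacy test uses these variables.

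**What to change.** In SAP 5.12:

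- Define change from baseline for anti-AQP4 titre, plasmablasts, CD19+ cells, IL-6, sIL-6R and hsCRP as the within-patient log ratio to baseline.
- Present the geometric mean ratio with 95% CI by arm and visit, and plot that ratio on the log axis.
- Delete the semi-log plots of signed differences.
- State a substitution rule for zero or BLQ PD values. The half-LLOQ rule in SAP 5.2 covers serum drug concentration only, and no rule covers a zero cell count.

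In SAP 7.6, keep the common ceiling of 65536 and add a footnote that changes above it are not visible.

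Apply the log ratio to whichever AQP4 assay is analysed. The SAP is tied to Protocol Version 8, and the Version 11 rationale moves samples to ELISA because the cell-based assay drifted. A log ratio does not remove drift, and ELISA results may not lie on fourfold steps.

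The cost is SAP wording, one decision on zero and BLQ values, and reprogramming of a set of PD tables and figures. No new data are needed.

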5.13 Immunogenicity

ADA subgroup using confirmatory sample status are defined as below.

- ADA negative subjects: subjects without positive ADA during study. If sample at baseline is missing and no sample after the the baseline is positive, the subject is defined as "ADA negative subjects".
- ADA unaffected subjects: subjects who have pre-existing ADA (POSITIVE at baseline) that was NOT boosted to a higher level after the post dose. "NOT boosted to a higher level" means that ADA titer after the baseline is <fourfold than the ADA titer at baseline.
- Treatment-boosted ADA subjects: subjects who have pre-existing ADA that was boosted to a higher level at least one time point after baseline "Boosted to a higher level" means as follow
 - 1) ADA titer after the baseline is greater fourfold than the ADA titer at baseline
- Treatment-induced ADA subjects: subjects who have positive ADA not at baseline but after the baseline. If sample at baseline is missing and at least one sample after the baseline is positive, the subject is defined as "Treatment-induced ADA subjects"

The immunogenicity will be analyzed using the SAF population.

- The numbers and proportions of subjects with positive ADA at baseline will be presented by treatment group and overall.
- The numbers and proportions of ADA negative subjects, ADA unaffected subjects, treatment-boosted ADA subjects, and treatment-induced ADA subjects will be

summarized. The numbers and proportions of transient ADA and persistent ADA will be summarized in the treatment-induced ADA subjects.

Transient ADA: 1) Treatment-induced ADA detected only at one sampling time point (excluding the last sampling time point) during the study or 2) treatment-induced ADA detected at two or more sampling time points during the study, where the period between first and last ADA-positive sampling time points is less than 16 weeks, and the subject's last sampling time point is ADA-negative.

Persistent ADA: 1) Treatment-induced ADA detected at two or more sampling time points during the study, where the period between first and last ADA-positive sampling time points is 16 weeks or longer or 2) where the period between first and last ADA-positive sampling time points is less than 16 weeks, and the subject's last sampling time point is ADA-positive or 3) treatment-induced ADA detected only at the last sampling time point.

- The numbers and proportions of patients with positive/negative anti-SA237 antibody and neutralizing antibody will be presented at Week 0 and Q4W in SA237 group by visit.
- A by-subject listing of anti-SA237 antibody (confirmatory judgment (positive/negative), titer, ratio of peak titer/baseline titer, and ADA subgroup), neutralizing judgment (positive/negative), and adverse events in the subject having anti-SA237 antibody at least once at any point in time.

5.14 Determination of Sample Size

Approximately 70 subjects need to be recruited and randomized in a 1:1 ratio to the two treatment groups (SA237 and placebo). The sample size considerations are based on the following assumptions:

- A two-sided log-rank test
- 80% power at the 5% significance level
- A 66.5% reduction in the risk of relapse, i.e. the TFR hazard ratio of SA237 over placebo is 0.335
- TFR in the placebo arm following an exponential distribution, with hazard rate for one year $h(t) = 0.4184$
- A 2-year dropout rate of 10%

Based on the assumptions, 26 TFR events are needed for the primary analysis. TFR events are defined as protocol-defined relapses confirmed by the CEC with EDSS/FSS assessment performed by the examining assessor within 7 days after relapse symptoms were reported to site by the subject. The maximum accrual rate is estimated to be approximately 8 subjects per month, after the FPI plus 8 months of ramp up. The 70 subjects enrolled over one year and followed for an additional one and a half year will provide 26 TFR events. The primary analysis will be performed once 26 TFR events have been observed. Sponsor will conduct blind review during the double-blind period and might take appropriate action based on blind review.

Since the annualized relapse rate (ARR) is the number of relapse counts observed when every subject is observed for a year and suppose that the distribution follows a Gamma-Poisson distribution and that the mean and variance ratio (variance / mean) is a constant value of $\sqrt{2}$. The ratio was estimated using MS trials' data^{1,2)} because there are no approved medications for NMO.

Because the mean ARR of NMO subjects is estimated at 0.753³⁾ and eligibility criterion 2 says more than one ARR subjects are selected, we calculate the zero-truncated mean of the Gamma-Poisson distribution with the mean of 0.75 and the mean and variance ratio of $\sqrt{2}$, then the baseline ARR is estimated at 1.6. The two phase III MS trials above reported that pre- and post- baseline ARR in the placebo group were 1.4 and 0.4, so the post-baseline ARR in placebo group in this trial is estimated at 0.5.

Using the proportion of zero under supposed ARR distribution, we estimate the relapse-free rate at a year in placebo group at 65.8%. The relapse-free rate is assumed to follow the exponential distribution with a constant hazard, and then we set the hazard for one year of 0.4184 in placebo group.

According to tocilizumab case report in NMO subjects, the pre- and post- baseline relapse counts were reduced from total 4 counts per 6 months to 1 count per 6 months. Then the pre- and post- baseline ratio of 0.25 is used as the estimation of the mean ARR ratio of tocilizumab compared with placebo. Moreover, the azathioprine's data showed the pre- and post- baseline mean ARR ratio was 0.33 (= 0.77/2.32, the mean ARR were estimated from the median ARR and the distribution supposition above) and the rituximab data showed the pre- and post- baseline mean ARR ratio was 0.125 (= 0.3/2.4), then we estimate the rituximab mean ARR ratio compared with azathioprine at 0.38 (= 0.125/0.33).

Under the assumption of ARR and relapse-free rate distribution above, the mean ARR ratio is coincided with the hazard ratio. Tocilizumab hazard ratio data (0.25) could have a possibility of overestimation because of the case report with only three subjects and the hazard ratio between rituximab and azathioprine (0.38) is the comparison with an active control, then we consider the SA237 hazard ratio compared to placebo should exist between 0.25 and 0.38. So we have set the SA237 hazard ratio compared with placebo at 0.335.

